5.4.5.2 Tumour lysis syndrome (TLS)/Laboratory signs of cell destruction

The presence of TLS will be mainly investigated via adverse event reporting (see [Section 7.8](#)). In addition, laboratory signs of cell destruction will be investigated based on the laboratory values uric acid, potassium, inorganic phosphate and creatinine. Laboratory signs of cell destruction may be considered present if within the time window of the day of BI 836826 infusion and the following 6 days two or more of these laboratory parameters are considered abnormal simultaneously. Simultaneously means that abnormality of these ≥ 2 lab parameters occurs within 24 hours within the 7 day window after BI 836826 infusion. The definition of abnormal laboratory values is given in [Table 5.4.5.2: 1](#) below. In case laboratory signs of cell destruction are observed, it will be checked whether an AE episode that may indicate clinical TLS is reported within the 7 day time window after BI 836826 infusion. For the respective UDAEC see [Section 7.8](#).

Table 5.4.5.2:1 Definition of abnormal lab values for laboratory signs of cell destruction

Laboratory parameter	abnormal value
Uric acid	$\geq 476 \mu\text{mol/L}$ AND increase from relative baseline by $\geq 25\%$
Potassium	Only if relative baseline is $< 6.0 \text{ mmol/L}$: value $\geq 6.0 \text{ mmol/L}$
Inorganic phosphate	$\geq 1.45 \text{ mmol/L}$ AND increase from relative baseline by $\geq 25\%$
Creatinine	Absolute increase from relative baseline by $26.5 \mu\text{mol/L}$ AND increase from relative baseline by $\geq 50\%$

Definition of relative baseline: relative baseline is the last laboratory value prior to BI 836826 infusion, ie. it will be derived for the four laboratory values separately for each infusion.

6. GENERAL ANALYSIS DEFINITIONS

6.1 TREATMENTS

In this Phase I trial, treatments are not randomised (open-label, dose escalation). Different dose levels of BI 836826 can arise. The data will be presented for all dose cohorts separately, where Korean patients will be presented as a separate dose cohort from Caucasian patients.

In addition, the results for all patients in total, all Caucasian patients in total, and all Korean patients in total will be presented.

To justify the MTD determination, DLTs occurring during the MTD evaluation period (very first infusion of BI 836826 until the day of second infusion in Course 1 + seven days) will be presented separately from those occurring during the complete on-treatment period.

“Analysing treatment” will be used for reporting of treatment emergent AEs and to differentiate between screening, on-treatment and post-study safety data. The inequalities start date \leq onset date of AE $<$ end date will determine whether the AE will be assigned to the “analysing treatment” or not.

For the on-treatment period and the MTD evaluation period, the initial trial medication assigned at the beginning of the first treatment course will be used as the label of the analysing treatment.

AEs that have an onset date during the screening or post-study periods will be displayed in separate listings from those occurred during the on-treatment period.

The actual planned dose of trial medication administered on the day each AE started will also be derived. This will be presented in patient listings, but will not be used for defining treatments for analysis.

Labels of each analysing treatment period, analysis numbers, the labels used for display in the tables and listings in the CTR, as well as codes, decodes, sort order and labels for each trial medication used in this trial are provided in the TSAP technical document “ADS Plan”.

6.2 IMPORTANT PROTOCOL VIOLATIONS

Due to the fact that this is a phase I study, no per protocol population is needed, however important protocol violations (PV) should be identified for patients in the treated set (see [Section 6.3](#)). Any PV which may affect safety, efficacy or the patient’s rights will be determined.

The following table defines the different categories of important PVs. If the data show other important PVs, this table will be supplemented accordingly latest at the blinded report planning meeting (BRPM).

Table 6.2:1 Important protocol violations

Category /Code	Description		Example/Comment	Excluded from
A		Entrance criteria not met		
	A1	Patient has condition that may cause additional risk from study medication	Ex 16 - 21,23,24	None
	A2	Patient has laboratory assessments that may cause additional risk.	Ex 9 – 14,	None
	A3	Patient is unable to comply with the protocol	Ex 22, 25	None
	A4	Patient does not have trial diagnosis or is not part of the target population	In 1 - 2, 4, 6-7, Ex 1 – 7, Ex 8	None
B		Informed consent		
	B1	Informed consent not given or too late	In 8	None
C		Trial medication and randomisation		
	C1	Drug not administered according to the protocol	Administration according to protocol="No" and medical review of associated comments	None
	C2	Drug not administered according to protocol	Individual pre-medication taken="No" and medical review whether premedication would have been required according to protocol	None

6.3 PATIENT SETS ANALYSED

The Screened Set (SCR) includes all patients who signed informed consent form and will be used to summarize patient disposition.

The Treated Set (TS) consists of all patients who received at least one application of the BI drug BI 836826. The TS will be used for all planned safety analyses.

Replacement of patients is defined in Section 3.3.4.1 in the CTP. The final list of replaced patients is supplied by the Trial Clinical Monitor (TCM) no later than at the last BRPM before the DBL.

No per protocol population will be used for analyses.

Study medication is defined as BI 836826.

First administration of study medication is defined as date of first administration of BI 836826.

6.5 POOLING OF CENTRES

This section is not applicable because centre/country is not included in the statistical model.

6.6 HANDLING OF MISSING DATA AND OUTLIERS

If not stated otherwise, missing data will not be imputed and remain missing. Potential outliers will be reported and analysed as observed.

Missing or incomplete AE dates are imputed according to BI standards (see [\(5\)](#)).

Missing data and outliers are handled according to 001-MCS-36-472 [\(2\)](#).

If the day of birth is missing, then the imputed days will be the 15th. If start of new NHL therapy date is incomplete (only month given), then the start date will be imputed with the 1st of month unless the first day leads to a date before the stop date of study medication, then the study medication stop date +1 will be imputed. If more than only the day is missing, dates will not be imputed.

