**Proprietary confidential information.**

**© 2016 Boehringer Ingelheim International GmbH or one or more of its affiliated companies. All rights reserved.**

This document may not - in full or in part - be passed on, reproduced, published or otherwise used without prior written permission.

Clinical disease status will be assessed at screening, at the administration of the first and the last of the 4 infusions and 3 weeks after the last infusion of a respective course with physical examination, clinical assessment of the B-NHL, and blood samples. CT scans in this trial will be performed in accordance with published guidelines for response evaluation in lymphoma ([R04-1585](#)) and correspond to the use in clinical practice ([section 5.1.2.2](#)). A CT scan will be done prior to treatment (may be performed up to 8 weeks (preferably 4 weeks) prior to first infusion), after 2 courses of treatment, (*i.e.* at week 13 +/- window), and just before the end of treatment (EOT) visit (*i.e.* week 25 +/- window). If the CT scans are not possible or available, magnetic resonance imaging can be used instead. However the same imaging methods should be used consistently throughout the trial. Bone marrow examination, PET scan and additional CT scans will be performed at the discretion of the investigator. Results of CT scan, optional PET scan or bone marrow examination performed during the conduct of the trial should be reported in the eCRF. After the EOT visit which may occur at the latest at week 26, the patient will enter the follow-up phase. During the follow-up phase, disease status evaluations (physical examination, clinical assessment of lymphoma, and blood samples) should be performed at least every 6 weeks until 6 months after the EOT visit, administration of new anti-lymphoma therapy or death, whatever occurs first. More frequent visits may be indicated, *e.g.* for follow-up of laboratory parameters or adverse events which have not been resolved at the EOT visit.

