### **3.3.4 Removal of patients from therapy or assessments**

#### **3.3.4.1 Removal of individual patients**

A patient has to discontinue trial drug administration in case

- A DLT occurs which does not recover to a degree that allows treatment continuation (see [4.1.4.3](#))
- Progressive disease or any other concomitant diagnosis/symptom develops resulting in an indication to start any other therapy for lymphoma, including deterioration of general condition

An individual patient is to be withdrawn from trial in case

- The patient withdraws consent. Patients are free to discontinue their participation in this trial at any time without the need to justify the decision
- The patient needs concomitant drugs that may interfere with the investigational product (please refer to [section 4.2.2](#))

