5.2.2 Other Secondary endpoints

Tumour size reduction (indicator lesions, spleen and liver nodules)

Tumour size reduction of indicator lesions, spleen nodules and liver nodules will be analysed separately as secondary endpoints as follows:

Tumour size reduction of indicator lesions will be analysed as secondary endpoint “Best % change from baseline in SPD” from imaging data.

Tumour size reduction of liver nodules will be analysed as secondary endpoint “Best % change from baseline in SPD” from imaging data.

Tumour size reduction of spleen nodules will be analysed as secondary endpoint “Best % change from baseline in SPD” from imaging data. Best overall response (according to investigator assessment):

Response will be assessed according to the Standardized or Revised Response Criteria for Malignant Lymphoma from 1999 ([[R04-1585](#)]). Each patient will be assigned to one of the

following categories:

- complete remission (CR)
- complete remission unconfirmed (CRu)
- partial remission (PR)
- stable disease (SD)
- progressive disease (PD)

Best overall response (CR, CRu, PR, SD, PD in this order) is defined as the best overall response obtained since the start of study treatment. Best overall response will be evaluated in two different ways: first, all responses as documented by the investigator (independent of the assessment procedure) will be evaluated. In a further analysis, only disease evaluations for which imaging data are available in the eCRF will be evaluated. In case PD is captured by the investigator, the response PD will be always considered as PD, independent whether imaging data is available at this timepoint or not. For both evaluations only response assessments prior to any further NHL therapy and until PD will be taken into account. For the calculation of the date of response: if patients would have their examinations contributing to the disease assessment over a number of days, the earliest date of the multiple examinations will be considered.

Progression free survival (PFS):

PFS is defined as the time from first administration of study medication until disease progression or death, whatever occurs first.

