Patients administered a new additional therapy for NHL recorded in the electronic case report form (eCRF) but not presenting with disease progression before the start of this new NHL therapy will be censored at the date of last response assessment during which the patient was evaluable and did not have the event before the new NHL therapy has started.

Patients not administered another NHL therapy and not presenting with disease progression or death during the trial will be censored at the date of the last response assessment during which the patient was evaluable and did not have the event.

A patient is said to have an evaluable response assessment if a response of CR, CRu, PR, SD or PD has been assigned.

The censoring rules and the applicable dates of outcome for PFS are given in the following table.

Table 5.2.2:1 Derivation rules for progression-free survival

Situation	Outcome (event or censored)	Date of outcome
Baseline and post-baseline disease assessment: disease progression or death without prior additional NHL therapy	Event	Date of first disease progression or death
Baseline and post-baseline disease assessment: disease progression or death and prior additional NHL therapy	Censored	Date of last response assessment before start of new NHL therapy
Baseline and post-baseline disease assessment: No disease progression or death without additional NHL therapy	Censored	Date of last response assessment
Baseline and post-baseline disease assessment: No disease progression or death with additional NHL therapy	Censored	Date of last response assessment before start of new NHL therapy
No baseline or post-baseline disease assessment: without death	Censored	Date of first administration of BI 836826
No baseline or post-baseline disease assessment: death on or before the first planned disease assessment (i.e. at week 4 assessment)	Event	Date of death
No baseline or post-baseline disease assessment: death after first planned disease assessment (i.e. at week 4 assessment)	Censored	Date of first administration of BI 836826

Remark: determination of the response status via disease assessment refers to any disease assessment via imaging or via physical assessment

Progression free survival (PFS) [in days] is therefore the time from first administration of study medication to the earlier date of disease progression or death (minimum date of disease progression or death – date of first administration of study medication + 1).

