Progression free survival (PFS) censored [in days] is therefore the time from first administration of study medication to the date of last response assessment (date of last response assessment – date of first administration of study medication + 1).

Failure free survival (FFS):

FFS is defined as the time from first administration of study medication until disease progression or death or start of next NHL therapy.

Patients not administered another NHL therapy and not presenting with disease progression or death during the trial will be censored at the date of the last response assessment during which the patient was evaluable and did not have the event.

The censoring rules and the applicable dates of outcome for FFS are given in the following table.

Table 5.2.2:2 Derivation rules for failure-free survival

Situation	Outcome (event or censored)	Date of outcome
Baseline and post-baseline disease assessment: disease progression or death or start of next NHL therapy	Event	Date of first disease progression or death or start of next NHL therapy
Baseline and post-baseline disease assessment: No disease progression, death or new NHL therapy	Censored	Date of last response assessment
No baseline or post-baseline disease assessment: no death or new NHL therapy	Censored	Date of first administration of BI 836826
No baseline or post-baseline disease assessment: death/next NHL therapy on or before the first planned disease assessment (i.e. week 4 assessment)	Event	Date of death/next NHL therapy
No baseline or post-baseline disease assessment: death/next NHL therapy after the first planned disease assessment (i.e. week 4 assessment)	Censored	Date of first administration of BI 836826

Remark: determination of the response status via disease assessment refers to any disease assessment via imaging or via physical assessment

Failure free survival (FFS) [in days] is therefore the time from first administration of study medication to the earlier of disease progression or death or start date of next NHL therapy. (minimum date of disease progression, death or start of next NHL therapy – date of first administration of study medication + 1).

Failure free survival (FFS) censored [in days] is therefore the time from first administration of study medication to the date of last response assessment (date of last response assessment – date of first administration of study medication + 1).

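### A month-only start of new NHL therapy is imputed without checking it against a documented PD, so a PD that came first can be censored in PFS and the FFS event dated too early

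*SAP*

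**What the plan says.** SAP 6.6 deals with a start of new lymphoma therapy for which only the month is known: "If start of new NHL therapy date is incomplete (only month given), then the start date will be imputed with the 1st of month". One exception guards against a start that would precede the end of trial drug: "unless the first day leads to a date before the stop date of study medication, then the study medication stop date +1 will be imputed". Neither 6.6 nor 5.2.2 compares the imputed date with a documented PD.

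The imputed date feeds three derivations in SAP 5.2.2:

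- **PFS (Table 5.2.2:1).** The situation "Baseline and post-baseline disease assessment: disease progression or death and prior additional NHL therapy" is censored, at the last response assessment before the new therapy.
- **FFS (Table 5.2.2:2).** The event is dated "Date of first disease progression or death or start of next NHL therapy".
- **Best overall response.** For both evaluations, "only response assessments prior to any further NHL therapy and until PD will be taken into account".

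The date needed for a check is collected: protocol 6.2.3.1 requires the date of first documentation of PD at the EOT visit, and protocol 6.2.3.2 asks for the date of progression during follow-up.

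**The concern.** When PD and new therapy fall in one month, the documents point to PD first. Protocol 3.3.4.1 lists as a reason to stop trial drug: "Progressive disease or any other concomitant diagnosis/symptom develops resulting in an indication to start any other therapy for lymphoma". Under protocol 3.2, follow-up disease evaluations stop at 6 months after EOT, "administration of new anti-lymphoma therapy or death, whatever occurs first", so a PD is not normally looked for after new therapy has begun. Moving the therapy to the start of the month therefore tends to reverse a true PD-then-therapy sequence.

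The records affected are progressions. Censoring them is informative and pushes PFS upward. The same imputation moves FFS earlier, so a gap between the two endpoints can appear in patients for whom PFS and FFS should coincide. Best overall response changes only where the PD was the sole evaluable post-baseline assessment; it then becomes missing.

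Patients who start new therapy without a documented PD are outside this point. So are same-month deaths, because therapy cannot start after death.

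**Working it through.** The plan gives no figure to reproduce here. The check applies the written rules to dates.

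**Inputs.** From the documents: the 6.6 rule, the two derivation tables, and the day count (date minus first administration plus 1). Also the assessment schedule in protocol 3.2: "at the administration of the first and the last of the 4 infusions and 3 weeks after the last infusion of a respective course". Assumed: the gap L from PD to therapy, the share of month-only dates, and that the stop date means the last infusion. Write d for the days from last dose to PD and p for the day of the month of PD.

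**Example 1, floor inactive (non-leap year).** First dose 29 January; fourth infusion and assessment 19 February (day 22); PD 12 March (day 43, 3 weeks after the last infusion); new therapy 26 March, recorded only as March. 1 March is not before 19 February, so the imputed start is 1 March (day 32).

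| | True dates | Under SAP 6.6 |
|---|---|---|
| PFS | event, day 43 | censored, day 22 |
| FFS | event, day 43 | event, day 32 |

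**Example 2, floor active.** First dose 11 January 2016; last dose and last assessment before PD 4 February (day 25); PD 22 February (day 43); therapy 26 February, recorded as February. 1 February is before the stop date, so the imputed start is 5 February. PFS is censored at day 25 instead of an event at day 43; FFS is an event at day 26. The floor does not prevent the error.

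**How often the order is reversed, per month-only record.** With d at least 2, PD and therapy must share a month of m days (p at most m − L) and PD must not be on the 1st. The share is (m − L − 1)/m. For m = 30: L = 7 gives 22/30 = 0.733; L = 14 gives 15/30 = 0.500; L = 21 gives 8/30 = 0.267. Applying the full rule to all 2,192 PD dates in 2012–2017 gives 0.737, 0.507 and 0.277, and 0.049 for L = 28.

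With d = 0 the floor puts therapy after PD, or on the same day if PD is on the 1st, so the share is 0. With d = 1 only a PD on the 2nd is reversed: about 1/30 = 0.033.

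On schedule d is normally 7 or more. Protocol 4.1.4.4 requires no evidence of PD before a further infusion, so a PD found at an infusion visit is at least a week after the previous dose, and the end-of-course assessment is 3 weeks after the last infusion.

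**How early FFS becomes.** If the 1st is used, the shift is p − 1 days; if the floor applies, it is d − 1 days. Among reversed records, for L = 7, 14 and 21:

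- d = 7: mean 5.4, 5.1 and 4.3 days (maximum 7).
- d = 27 or 55: mean 11.7, 8.2 and 4.8 days (maximum 23, 16 and 9). At d = 21 the means are 11.6, 8.2 and 4.8.

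**Effect on the PFS curve (illustration only).** Exponential PFS with an assumed 3-month median; assessments on days 22, 43, 50, 71, 92, 99, 120 and 175, then every 42 days; L uniform on 3–28 days; every patient progresses and then starts therapy; 600 runs per setting. N = 53 is the protocol 7.6 total (41 + 12); N = 16 is the Korean maximum (4 + 12).

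| N | Month-only share | PDs censored | Median PFS (days) | 6-month PFS (%) |
|---|---|---|---|---|
| 53 | 5% | 1.1 | 105 → 108 | 26.4 → 27.2 |
| 53 | 10% | 2.2 | 105 → 110 | 26.5 → 27.9 |
| 53 | 20% | 4.4 | 106 → 117 | 26.6 → 29.5 |
| 16 | 10% | 0.7 | 99 → 106 | – |
| 16 | 20% | 1.4 | 99 → 114 | – |

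Hand check of the counts: mean L is 15.5, so the mean reversal share is about (30.44 − 15.5 − 1)/30.44 = 0.458. Then 53 × 0.458 × 0.05, 0.10 and 0.20 gives 1.2, 2.4 and 4.9, close to the simulation.

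**The case against.** The strongest reply is that the trigger is narrow and the consequence small.

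- **Frequency.** The protocol asks for the date of new therapy (6.2.3.1, 6.2.3.2) and accepts month and year only for prior history (5.3.2.1). The 6.6 rule is a fallback, and nothing in the documents supports a share of 5, 10 or 20%. This stands: the count is unknown and may be zero.
- **Illustration near its upper bound.** It lets every patient progress and start therapy within 28 days. Deaths, longer gaps and untreated patients all reduce the loss. This stands.
- **Precision.** With about 48 events, an approximate 95% range for an exponential median is a factor exp(±1.96/√48), or 0.75 to 1.33: about 79 to 139 days around 105. A shift of 3 to 11 days is well inside that. True, but the shift is a one-directional bias that can be removed at almost no cost.
- **Order unknown.** Protocol 5.1.2.4 expects some patients to start next therapy before any formal PD, and Table 5.2.2:1 has a row for PD after therapy. Declaring PD first could misclassify such a patient. This stands in part, but because evaluations end at new therapy, it is the less common order to find documented.
- **Protocol 7.4** excludes imputation of missing efficacy data, and a new-therapy start is an FFS event date. That tension already exists in the 6.6 rule and is separate from this point.
- **References.** SAP 6.6 also cites an internal standard not available here; its listed title concerns pharmacodynamic analyses. The visible SAP text does not define the stop date; last infusion is the natural reading.

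None of this removes the mechanism.

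**Conclusion.** The concern holds. As written, the rules can turn an observed progression into a censored PFS time and date the FFS event before the progression that prompted the therapy. This is a stated rule giving a wrong result, not a missing detail.

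Confidence is high in the mechanism and in the per-record shares, which depend only on the calendar and the assumed gap. The curve-level effect is conditional on the assumed number of month-only dates, the 3-month median and gaps of 3–28 days. Under those near-upper-bound assumptions it is about 1 to 5 lost events and 3 to 11 days of median PFS in all 53 patients, and about 1 lost event and 7 to 15 days in the Korean total at shares of 10–20%.

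PFS and FFS are secondary and descriptive, and no formal tests are planned. MTD, DLT counts and dose escalation are not affected. The change should be made because the bias has a known direction and the correcting date is already collected.

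**What to change.** Keep the present imputation and add to SAP 6.6: if a PD is documented in the same month as a month-only start of new NHL therapy and is later than the imputed date, the start is set to the PD date; this PD counts as occurring before the new therapy for PFS, FFS and best overall response.

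The adjusted date stays within the recorded month, and the second clause settles the same-day tie. Applied to the same calendar of PD dates, it leaves no reversed record. In both examples PFS and FFS return to events on day 43.

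The cost is one sentence in SAP 6.6 and the matching line in the derivation program. No new data are needed.
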